Study intervention: The intervention in this investigation will be implemented for all allogeneic RBCs administered on the day of surgery (intraoperative and postoperatively on Study Day 1). The decision to administer an allogeneic RBC transfusion will be left to the responsible clinical service and will not be prespecified in the study protocol. We have elected to leave this decision to the clinical service for the following reasons: 1) the target population frequently experiences major acute blood loss; in these circumstances, typical measures assessing the need for RBC transfusion (e.g. Hb) are often associated with unacceptable time delays and frequently do not reflect true red blood cell mass nor need for RBC transfusion; 2) this design facilitates a more meaningful understanding of the feasibility of RBC washing in clinical practice. Upon receiving an order for allogeneic RBC transfusion, the transfusion medicine service will prepare the RBC product according to the allocated treatment assignment (intervention versus control). Of note, all allogeneic RBC units at the two participating institutions undergo pre-storage leukocyte reduction.

Intervention cohort: For patients randomized to receive washed RBCs, all allogeneic RBCs **administered** on the day of surgery will be washed with the CATS device prior to transfusion. To account for the time

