required to complete the ordering, delivery, washing, and administration procedures, we will restrict RBC washing to those RBC units ordered prior to 23:30 on the day of surgery. Any RBC unit ordered after 23:30 on the day of surgery will no longer be considered an “intervention unit” and will therefore be standard issue (non-washed) as it anticipated that the time required to perform the activities mentioned above (ordering, delivery, washing, and administration) would otherwise result in the RBC component’s actual administration time to occur on the day after surgery. When the need for transfusion is identified by the primary team, the RBC product will be prepared. As previously described⁸ and confirmed in our preliminary data, pre-dilution of stored, allogeneic RBCs results in the most effective elimination of supernatant. Therefore, an approximate 4:1 dilution will be added to the reservoir of the CATS by gravity drainage. The “High Quality” wash mode option will be selected for processing; this takes approximately 7-10 minutes to complete.⁷⁴ Washed RBCs will then be drained from the reinfusion reservoir into sterile transfer bags (Fenwal Inc, Lake Zurich, ILL) for transfusion.

-Control cohort: For patients randomized to the control group arm, all RBCs administered on the day of surgery will be standard-issue RBCs.

Off-protocol transfusions: In the setting of cardiac surgery, it is occasionally necessary to provide allogeneic RBCs in an emergent fashion (e.g. acute, life-threatening bleeding). In this particular circumstance, time-delays relating to study-related activities may prove unsafe. To address this potential scenario, our study protocol will allow the administration of emergency “off-protocol” allogeneic RBCs. “Off-protocol” RBC transfusions will be administered as per standard institutional practice. These RBC transfusion episodes will be specifically noted as “off-protocol” and will be summarized and analyzed to assist in assessing the feasibility of point-of-care RBC washing in patients undergoing cardiac surgery (see statistical description below). In addition, autotransfusion (“cell-saver”) is frequently used in this patient population. Cell-salvage will be implemented at the discretion, and under the direction, of the clinical team. If cell-salvage is employed, the device used for this procedure will be distinct and separate from the intervention CATS device.

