Specific Aim 1: The **primary feasibility outcome in aim 1a** will be the number and proportion of "off-protocol" allogeneic RBC transfusions administered during the study intervention period (day of surgery). A secondary feasibility outcome will be the time required for the RBC washing procedures (defined as the time from determination of RBC need by the clinical team to time of delivery of the RBC unit to the clinical team). This time will be computed for all patients and all transfusions during the study intervention period (in both the intervention and control cohorts). The **primary safety outcome in (aim 1b) include** the change in the RBC recipient's Hb concentration from pre- to post-transfusion as well as the concentration of CFH and haptoglobin following RBC transfusion. To assess the primary safety outcomes, samples for total Hb, CFH, and haptoglobin will be obtained prior to transfusion, as soon as possible after the first transfusion, but no later than 30 minutes following the first intervention/control RBC transfusion, as well as 6 hours (+/- 30 minutes) and 18 hours (+ / - 30 minutes) from the end of first study RBC transfusion for all study participants. We will also assess for clinical evidence of acute kidney injury throughout the hospitalization. Safety labs will also be drawn anytime on study day #5 if the patient is still in the hospital. The **primary efficacy outcome in aim 1c** will be the change in the concentration of neutral lipids [arachidonic acid, 5-hydroxyeicosatetraenoic acid (HETE), 12-HETE, 15-HETE], sCD40L, CCL5/RANTES, RBC-MPs, and CFH in the RBC component from the pre- to the post-wash phase. These data will allow us to calculate the CATS-related elimination rates for these BRMs, which have previously been associated with transfusion-related respiratory dysfunction and hemodynamic alterations. To balance assay costs while ensuring the scientific success of aim 1c, pre- and post-wash samples will be obtained/analyzed for the first 75 washed RBC units. If efficacy is not clearly established, we will continue to obtain both pre- and post-wash samples for 75 additional units.

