Specific Aim 2: The outcomes measures for aim 2a will be the change in concentration of multiple, validated lung injury biomarkers representing the primary pathways leading to development of lung injury (Table 5). Patients will have blood drawn as soon as possible after the decision to transfuse, as soon as possible after transfusion, but not later than 30 minutes after the end of first study RBC transfusion, 6 hours (+ / - 30 minutes) from the end of first study RBC transfusion, and 18 hours (+ / - 30 minutes) from the end of first study RBC transfusion.

Table 5. Lung injury biomarkers and exploratory potentially pathogenic biologic response modifiers for specific aim 2.

Validated lung injury biomarkers (Aim 2a)	Primary process evaluated	Supporting Reference
Interleukin-6	Inflammation	77-79
Interleukin-8		77-81
Von Willebrand Factor	Endothelial activation/injury	77,80-8570,73-76
Intercellular Adhesion Molecule-1		77,80,86-89
Receptor of Advanced glycation end-products	Epithelial Injury	80,93
Surfactant Protein-D		77,80,90,91
Plasma activator inhibitor-1	Dysregulated coagulation	79,86,94-96
Exploratory biomarkers (Aim 2c)	Primary process evaluated	Supporting Reference
Neutral lipids	Lung inflammation	6,12
sCD40L		3
CCL5/RANTES		13,29,30
RBC-derived microparticles	NO scavenging	16-18
Free Hemoglobin		18-20
N-terminal Brain Natriuretic Peptide	Ventricular stretch/volume-overload	97-99

In addition to these biomarker analyses, we will proceed with detailed assessment of the cardiopulmonary responses to study RBC transfusions administered in the operating room (**Aim 2b**). Specific variables to be assessed and recorded are listed in Table 6. Systemic vascular resistance will be calculated at each time point using the following equation: $SVR \text{ (dyns/cm}^5\text{)} = [(MAP - RAP)/CO] \times 80$. Each of these variables will be assessed and recorded immediately prior to the intervention RBC transfusion and again immediately after the RBC transfusion. Standard operating procedures for these cardiopulmonary assessments will be defined prior to study onset according to previously established recommendations.¹⁰⁰ These secondary outcomes will allow a more detailed assessment of the cardiopulmonary response to RBC transfusion and will be expected to provide important insight into the pathophysiology of TACO. Of note, pulmonary artery catheter placement is standard of care for this patient population at both of the enrolling institutions.

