Specific Aim 3: To facilitate the design and conduct of future clinical trials, we will also pursue a number of exploratory clinical outcomes. **The clinical outcome measure of interest for aim 3** is the duration of postoperative mechanical ventilation. Study coordinators will collect data daily until endotracheal extubation, death or hospital discharge regarding the need for mechanical ventilation. The primary clinical outcome will then be determined by calculating the duration of mechanical ventilation in hours for each study participant, determined by subtracting the time of ICU admission from the time of endotracheal extubation. If the study participant is extubated prior to ICU admission, the duration of mechanical ventilation will be assigned as 0 hours. Recognizing the potential for early death (intraoperative or early postoperative) biasing our primary clinical outcome, the number of ventilator free days (VFD) at postoperative day 28 will also be determined. Those who die prior to day 28 will be determined to have had 0 VFD. Those who are discharged from the hospital alive prior to day 28 will be assumed to have had no additional days of mechanical ventilation following hospital discharge. Additional secondary outcomes for Aim 3 will include evaluations of hypoxemia (SpO_2 , PaO_2/FiO_2), duration of oxygen supplementation, sequential organ failure assessment scores, and durations of ICU and hospital stay. The clinical diagnoses of TRALI, possible TRALI, and/or TACO will be measured through study day 5, or hospital discharge, whichever comes first.

Specimen Handling and Laboratory Assays: Aim 1b: 5 ml of blood will be drawn from each study participant at baseline, following the first RBC unit administered, 6 hours after the end of the first RBC transfusion, 18 hours after the end of first RBC transfusion, and on hospital day 5 if the patient remains hospitalized (see **Specific Aim 1** and **Specific Aim 2** for more details on the timing of blood draws). These safety laboratory

Table 6. Physiologic parameters to be measured during the study intervention period.	
Respiratory Variables	Hemodynamic Variables
PaO_2 , SpO_2 , FiO_2	Mean arterial pressure
Tidal Volume	Heart Rate
Peak inspiratory pressure	Cardiac output
Plateau airway pressure	Central venous/right atrial pressure
Positive end-expiratory pressure	Pulmonary artery wedge pressure

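### The baseline blood draw is tied to the decision to transfuse, so the wash lengthens the pre-to-post interval in the washing arm only and can bias the first-unit hemoglobin comparison

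*Combined protocol and SAP*

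**What the plan says.** **Baseline, Aim 2.** Outcome Measures, Specific Aim 2: "Patients will have blood drawn as soon as possible after the decision to transfuse".

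**Post draws, Aim 2.** The first is due "not later than 30 minutes after the end of first study RBC transfusion". The next two come 6 and 18 hours (each within 30 minutes) after the end of that transfusion.

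**Baseline, Aim 1b.** Outcome Measures, Specific Aim 1: "samples for total Hb, CFH, and haptoglobin will be obtained prior to transfusion". No maximum gap before the start of transfusion is given. Specimen Handling and Laboratory Assays sends the reader to both Specific Aim 1 and Specific Aim 2 "for more details on the timing of blood draws", and the Table of Events has a single baseline research draw.

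**What lies between the two anchors.** Under Intervention cohort, the unit is prepared once the need is identified. It is diluted, drained into the device by gravity, washed and drained into a transfer bag. Of the wash mode the text says "this takes approximately 7-10 minutes to complete"; the other steps have no stated duration.

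**Delay as an outcome.** A secondary feasibility outcome, computed in both arms, is "the time from determination of RBC need by the clinical team to time of delivery of the RBC unit to the clinical team". No analysis of hemoglobin or biomarkers uses it.

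**A different anchor for Aim 2b.** Hemodynamic and respiratory readings are taken "immediately prior to the intervention RBC transfusion and again immediately after the RBC transfusion".

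**Analyses.** Statistical Considerations makes hemoglobin change after the first unit the primary safety measure, compared by Wilcoxon rank sum test. For Aim 2 the main parameter is the group-by-time interaction in a linear mixed model. The text does not say whether actual or nominal draw times enter that model.

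**The concern.** A change score compares like with like only if the time between its two measurements does not depend on treatment. Here it does. A coordinator who follows the Aim 2 instruction draws before or during the wash, so the washing arm carries extra minutes that controls do not have. Randomization does not protect against this, because the extra time is a consequence of assignment.

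Those minutes may not be quiet ones. Study intervention says that "the target population frequently experiences major acute blood loss", and that hemoglobin then often fails to reflect red cell mass. If hemoglobin is falling, the washing arm's rise after the first unit is understated. That would look the same as red cells lost in the wash, which is the question Aim 1b asks. The first post-transfusion biomarker draw is exposed in the same way, because its interval is also short.

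**Working it through.** **1. The plan's own figure.** Sample Size Considerations gives 78 per group for an effect of 0.4 SD at two-sided alpha 0.10. Power for Aim 2a is not stated; I assume 80%.
n = 2 × (1.645 + 0.842)² / 0.4² = 77.3, rounded up to 78. The figure reproduces. Power is 80.3% at 78 per group and 79.9% at 77, the latter being half of the 154 transfused patients at which enrollment stops. The timing issue does not alter this sample size.

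**2. Length of the asymmetry.** The only documented component is 7-10 minutes. Against assumed control-arm intervals from baseline to the first post draw:

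| Interval | Added by 7 min | Added by 10 min |
|---|---|---|
| 30 min (assumed) | 23% | 33% |
| 60 min (assumed) | 12% | 17% |
| 90 min (assumed) | 8% | 11% |
| 6 h | 1.9% | 2.8% |
| 18 h | 0.6% | 0.9% |

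The first post draw is where the extra time matters.

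**3. Hemoglobin change after the first unit.** The documents give no drift rate and no SD of change. Assumptions: SD 1.0 g/dL, 77 per arm, and the same drift of 0.25-1.0 g/dL per hour, in one direction, in both arms.
- Bias = drift × extra minutes / 60.
- SE = 1.0 × √(2/77) = 0.161 g/dL.
- False-positive rate = Φ(bias/SE − 1.645) + Φ(−bias/SE − 1.645), a normal approximation standing in for the Wilcoxon test.

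| Extra time | Drift (g/dL per h) | Bias (g/dL) | Bias/SE | False-positive rate |
|---|---|---|---|---|
| 7 min | 0.25 | 0.03 | 0.18 | 11% |
| 7 min | 0.5 | 0.06 | 0.36 | 12% |
| 10 min | 0.5 | 0.08 | 0.52 | 14.5% |
| 10 min | 1.0 | 0.17 | 1.03 | 27% |

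The nominal rate is 10%. With no drift the bias is zero.

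**4. Aim 2 slope to 18 hours.** Take draws at 0, t₁, t₁ + 6 h and t₁ + 18 h, with t₁ assumed to be 0.5-1.5 h. Suppose the washing arm's baseline is really d hours earlier but is coded as time 0, and both arms share a linear drift β. Least-squares weights give a spurious difference in slope of β × d × t̄ / Σ(t − t̄)². For t₁ = 0.5 h, t̄ = 6.375 and Σ(t − t̄)² = 222.2.
- 7 min: (7/60) × 6.375 / 222.2 = 0.33% of β.
- 10 min: 0.48% of β.
- 30 min (an assumed upper case): 1.43% of β.

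With t₁ = 1.5 h the values are 0.35%, 0.50% and 1.51%. With actual times and truly linear drift the spurious slope is zero. A steep, nonlinear perioperative change could make it larger.

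**The case against.** **Bias is a possibility, not a finding.** It needs a net drift in the added minutes, and the documents give neither rate nor direction. Blood loss suggests a fall in hemoglobin. But Off-protocol transfusions says cell salvage is often used in these patients, and returned red cells could offset a fall. This stands: a reader might infer that the timing necessarily works against washing, and the documents do not support that.

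**Large figures rest on assumed corners.** With a 30-minute gap and a drift of 1.0 g/dL per hour, the formula gives a bias of 0.50 g/dL and a false-positive rate of 93%. Both inputs are assumed extremes. Handling does add time beyond 7-10 minutes, but the amount is not stated, so that figure should not be used to size the problem.

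**The biomarker analysis is mostly safe.** A reader might infer that the main Aim 2 result is distorted too. Step 4 shows a shift of 0.3%-1.5% of the common slope under linear drift. What remains is the first post-transfusion draw and any steep nonlinear change.

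**The link to hemoglobin is indirect.** The Aim 1b text says only that samples precede transfusion; the decision anchor arrives through the cross-reference and the single baseline draw. The Aim 2 wording also allows a draw during the wash, so the extra gap varies. Both points are fair. Still, even on the Aim 1b text alone, nothing limits the gap or makes it equal between arms.

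**The delay will be visible.** Need-to-delivery time is computed in both arms, which helps interpretation. It is not the baseline-to-post interval, and no planned analysis uses it.

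**A late baseline may be lost.** Waiting for the unit could miss baselines when it is hung quickly, more often in controls, where no wash delays delivery. This stands and shapes the fix.

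**Conclusion.** The point holds in a limited form. Following the text as written gives unequal pre-to-post intervals by arm, of about 7-10 minutes plus unstated handling time when the draw precedes the wash. This can bias the primary safety comparison and the first post-transfusion biomarker comparison if the quantity measured is changing at the time. Under the stated assumptions (SD 1.0 g/dL, 77 per arm, common drift of 0.25-1.0 g/dL per hour) the hemoglobin bias is 0.03-0.17 g/dL and the false-positive rate about 11%-27% instead of 10%. The direction is open. The effect on the Aim 2 slope to 18 hours is small under linear drift. The change is worth making because it costs little and the protocol already uses a pre-transfusion anchor for Aim 2b.

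**What to change.** - **Anchor.** In both arms, take the baseline research draw as close as practicable before the start of the first study RBC infusion, and never after it starts. State that this applies to the Aim 1b and Aim 2 samples alike.
- **Fallback.** Where the unit may be hung at once, draw early, keep that sample and flag it. The fallback has to be used in advance, since a baseline cannot be recovered once infusion has begun.
- **Times.** Record the times of the decision, each draw, and the start and end of infusion.
- **Models.** Use actual draw times in the Aim 2 mixed models.
- **Reporting.** Show the baseline-to-start and baseline-to-post intervals by arm next to the hemoglobin comparison. Add a sensitivity analysis limited to baselines drawn shortly before infusion, with that window set in advance.

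The cost is wording, time stamps on the form, and a few early or missed baselines, which should be counted by arm. The sample size does not change.

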Table of Events

Event	Study Day 1	Study Day 2	Study Day 3	Study Day 4	Study Day 5	Study Day 6-28
Baseline Research Blood Draw	X					
Research Blood Draw #2	X*					
Research Blood Draw #3 (6 hours)	X*					
Research Blood Draw #4		X				X
Research Blood Draw #5						X
Daily Assessment for ARDS/TRALI / TACO	X	X	X	X	X	
Monitoring of blood products	X	X	X	X	X	X
Oxygen titration monitoring**	X	X	X	X	X	X
Adverse Event Monitoring	X	X	X	X	X	X

*May actually occur on the next study day if the patient is a late surgical case

**Oxygen titration only occurs on extubated patients

A. Specific Aims

With the **long-term goal** of reducing pulmonary morbidity following perioperative transfusion, **the objective of this proposal** is to test the feasibility, safety, efficacy, and clinical impact of point-of-care washing of allogeneic Leukocyte-Reduced (LR) Red Blood Cells (RBCs). Specifically, we will evaluate the impact of this intervention on intermediate mechanistic and physiologically-relevant markers of transfusion-related acute lung injury (TRALI) and transfusion-associated circulatory overload (TACO). To this end, we propose a multicenter, randomized, phase I/II clinical trial in adult cardiac surgery patients receiving LR-RBCs on the day of surgery.

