Blinding: In light of the time-sensitive, point-of-care nature of the intervention being proposed, the patient, clinical team, and members of the study team involved in the RBC washing procedure will not be blinded to the patient’s treatment allocation status. Blinding will be ensured for Drs. [name] and [name] who will be running the proposed biomarker analyses.

Other aspects of care: ARDSnet trials have demonstrated the benefit of standardizing clinical processes in ICU trials.^{75,76} In this study, clinical care that may affect development of respiratory dysfunction and associated outcomes will be standardized to the extent possible. To this end, our protocol will specify optimal ventilator strategies for both the OR and ICU environments (tidal volume \leq 8 mL/kg predicted body weight; peak inspiratory pressures $<$ 35 cm H₂O, PEEP \geq 5 cm while ventilated in the ICU). Similarly, although we will not pre-specify RBC transfusion thresholds in this protocol, we will advise restrictive transfusion practices in the postoperative period (hemoglobin target $>$ 8 g/dL in the absence of acute bleeding and/or ischemia). This transfusion threshold was chosen as it is the current standard of care at the two participating institutions. Standardization of best practices in at-risk patients will decrease the heterogeneity of the risk modifiers that may otherwise confound our associations of interest (RBC washing and intermediate markers of respiratory outcomes). Additionally, each center has adopted protocols on daily spontaneous awakening and spontaneous breathing trials to facilitate standardized weaning from ventilators (see attached appendix for specific protocols). Non-intubated patients will undergo standard titration of oxygen twice daily (at 0700 and 1900, +/- 2 hours). Patients saturating 92% or greater on room air will not receive supplemental oxygen, unless specifically requested by the primary service. If the primary care service requests oxygen supplementation for a patient saturating greater than or equal to 92% on room air, the reason for the deviation from oxygen weaning will be documented. Patients will continue to undergo evaluation for oxygen titration until liberation from oxygen therapy for 24 hours, hospital day 28, or hospital discharge, whichever comes first.

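### Required ventilation data stop at extubation, so day-28 ventilator-free days are overstated for reintubated patients alive at day 28

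*Combined protocol and SAP*

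**What the plan says.** The ventilation outcomes are set out under Outcome Measures, Specific Aim 3, in the combined protocol and SAP.

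- **Collection.** "Study coordinators will collect data daily until endotracheal extubation, death or hospital discharge regarding the need for mechanical ventilation". Nothing says that collection restarts if a patient is ventilated again.
- **Duration.** This is one interval, "determined by subtracting the time of ICU admission from the time of endotracheal extubation". A patient extubated before reaching the ICU is given 0 hours.
- **VFD.** Because early death could bias duration, "the number of ventilator free days (VFD) at postoperative day 28 will also be determined".
- **Scoring rules for VFD.** For deaths: "Those who die prior to day 28 will be determined to have had 0 VFD". Patients who leave hospital alive before day 28 "will be assumed to have had no additional days of mechanical ventilation following hospital discharge".

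Some other follow-up runs past extubation. Under Other aspects of care, oxygen titration checks go on "until liberation from oxygen therapy for 24 hours, hospital day 28, or hospital discharge, whichever comes first". A footnote to the Table of Events adds: "Oxygen titration only occurs on extubated patients". The Table of Events also marks adverse-event and blood-product monitoring for study days 1 to 5 and 6 to 28. Specific Aim 3 lists organ failure scores, ICU stay, and TRALI and TACO diagnoses to study day 5 or discharge. None of these is named as a source of ventilator days. The text supplied does not mention reintubation.

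**The concern.** A 28-day VFD count needs each patient's ventilator status on every day to day 28. The plan supplies a rule for death and a rule for time after live discharge. Because the second rule is confined to time after discharge, it implies that status in hospital is known up to that point. The stop rule does not provide this: between extubation and discharge there is neither a required observation nor a scoring rule.

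The resulting error has one direction. A reintubated survivor looks ventilator-free from the recorded extubation onward, so VFD can only be too high. It falls on patients whose breathing fails after extubation, who are of direct interest here. The problem statement in B1 says that most TRALI patients need ICU admission and ventilator support, typically for 3 to 10 days. Under Study intervention, study units include those given postoperatively on day 1, so exposure can follow an extubation. The Aim 3 paragraph of Statistical Considerations says that these estimates are to inform the design of later trials.

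**Working it through.** **1. The plan's own figure.** The documents give no figure for VFD or reintubation. The only sample size for comparing arms is 78 per group (Sample Size Considerations), based on the Aim 2a biomarkers: effect 0.4 SD, two-sided alpha 0.10, equal allocation. Power is not stated for this figure; 80% is inferred because it reproduces the number.

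n = 2(1.645 + 0.842)² / 0.4² = 77.3, rounded up to 78 per group (90% power would give 108).

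VFD does not enter this calculation, so the point leaves it unchanged.

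**2. What the text covers, period by period.**

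| Period up to day 28 | Ventilation status required? | Scoring rule for VFD |
|---|---|---|
| Up to extubation | Yes, daily | Counts as ventilated |
| Extubation to discharge, or to day 28 if still in hospital | No | None |
| After live discharge | No | No ventilation assumed |
| Death before day 28 | Not needed | Score set to 0 |

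Only the second row has neither data nor a rule.

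**3. One patient (assumed course).** Extubated on day 1, reintubated at the end of day 3, ventilated for d further days, alive at day 28.

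- From the recorded extubation: 28 − 1 = 27, whatever d is.
- Counting all unassisted days: 28 − 1 − d = 24, 20 or 13 for d = 3, 7 or 14.
- Counting only days after the last extubation: 28 − (3 + d) = 22, 18 or 11.

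The overstatement is d days on the first definition (3, 7 or 14). On the second it is d + 2 days (5, 9 or 16), because the two unassisted days between episodes also drop out.

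**4. Mean of an arm.** Let r be the share of an arm who are reintubated survivors, and d the missed ventilated days each, up to day 28. Counting all unassisted days, the overstatement is r × d. Both inputs are assumptions.

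- 0.02 × 3 = 0.06 days
- 0.05 × 7 = 0.35 days
- 0.10 × 14 = 1.4 days

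With 154 / 2 = 77 patients per arm, 2% to 10% is 0.02 × 77 = 1.5 to 0.10 × 77 = 7.7 patients.

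**5. Difference between arms.** If washing halved reintubation and d were equal in both arms, the VFD difference lost would be (control rate − washed rate) × d.

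- Smallest case: (0.05 − 0.025) × 3 = 0.075 days
- Largest case: (0.10 − 0.05) × 14 = 0.70 days

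If the rates and d were equal in both arms, both means would be too high but their difference would be unbiased.

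**The case against.** **The word first is not in the rule.** Extubation could be read as the final one, and patients are still followed in hospital afterwards, so finality could be established. On that reading VFD could be computed. But a coordinator cannot tell on the day that an extubation is final. Collection would have to go on after every extubation, and the rule does not ask for that.

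**A reader might infer that reintubation is never recorded.** The documents do not support this. Adverse-event monitoring, organ failure scores, TRALI and TACO assessment, or a break in oxygen titration could each reveal one. What stands is narrower: none is named as an input to VFD, and none is required to give start and stop times. Oxygen checks can end 24 hours after liberation from oxygen, and TRALI and TACO assessment ends by study day 5. The case-report forms and operating procedures are not in the supplied text and may say more.

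**A reader might infer that VFD is wrong for everyone with respiratory failure, or that the trial loses sight of TRALI and TACO.** Neither holds. Deaths before day 28 score 0 regardless, a single unbroken episode is counted correctly, and TRALI and TACO are separate outcomes.

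**The duration outcome is computable as defined.** This stands. Summing hours over all episodes would be a different estimand, not a correction.

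**Aim 3 is exploratory and carries no power calculation.** This also stands, and it limits the consequence. It does not remove it, since informing later trials is the stated use of these estimates.

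**Conclusion.** The point holds for VFD. The collection rule and the day-28 outcome do not fit together, and following both as written overstates VFD for reintubated patients alive at day 28. This is more than missing detail, because the stated stop rule leads to a wrong count.

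The size cannot be derived from the documents. The range of about 0.06 to 1.4 days in an arm's mean rests entirely on the assumed rates of 2% to 10% and the assumed 3 to 14 missed days, counting all unassisted days. At the low end it is negligible and involves one or two patients per arm. At the high end it could matter to someone using these data to plan a trial.

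It would be wrong to infer that the trial's main comparison is compromised: the sample size and the Aim 2 analysis are unaffected. The change is worth making, but it concerns an exploratory outcome.

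**What to change.** Under Specific Aim 3:

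1. Record ventilation status daily to the earliest of hospital discharge, death and postoperative day 28, with start and stop times for every episode.
2. Compute VFD from all episodes, and state whether it counts all unassisted days or only those after the last extubation. The example above differs by two days between these definitions.
3. Keep the existing duration outcome if wished, labelled as the initial episode, and report total hours over all episodes beside it.

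The cost is one additional daily item for inpatients. Blood-product use is already recorded to day 28 or discharge (Predictor variables other than the intervention), and the Table of Events schedules adverse-event monitoring over days 6 to 28. The oxygen titration record could not carry the item alone, because it may close earlier. Times of later episodes are needed only for patients who are ventilated again. The sample size does not change.
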